### 9.3.6 Week 6 Visit

Individual subject data (up to Week 6) will be cleaned and locked after the Week 6 visit. Following data lock, individual subject's randomized treatment assignment will be unblinded and the subject will be informed at the Week 10 visit.

At the Week 6 visit, the following activities/procedures will be performed:

- Vital signs (heart rate and blood pressure should be assessed in a seated position after 5 minutes of rest and prior to blood draws)
- AE review
- Concomitant medication review
- Hb using HemoCue
- Laboratory procedures:
  - CBC
  - Serum chemistry and eGFR
  - Iron indices
  - Hepcidin
  - C-reactive protein
  - VEGF
- Dispense blinded study drug (as necessary)
- Subjects should be questioned regarding dosing compliance
- Review dosing instructions

### 9.3.7 Week 10 Visit (End-of-treatment visit for the blinded period and early withdrawals)

All enrolled subjects who receive at least 1 dose of blinded study drug should complete the Week 10 assessments.

Subjects who withdraw early from the study prior to the Week 6 visit or permanently discontinue study medication prior to the Week 6 visit, should undergo the clinical and laboratory assessments specified below within 1 day of stopping study medication, if possible. Such subjects should also complete the requisite 2-week safety follow-up period (see [Section 9.3.10](#)).

Individual subject data (up to Week 6) will be locked after the Week 6. Following data lock, individual subject's randomized treatment assignment will be unblinded and the subject will be informed at the Week 10 visit. Subjects who were assigned to receive placebo will discontinue from the study at the end of the Week 10 visit, and subjects who were assigned to receive vadadustat will continue to the open-label extension period.

At the Week 10 visit, the following activities/procedures will be performed:

- Vital signs (heart rate and blood pressure should be assessed in a seated position after 5 minutes of rest and prior to blood draws)
- AE review (see [Section 10.3.6](#) for follow-up of unresolved events)
- Concomitant medication review
- Laboratory procedures:
  - Hb using HemoCue for dose adjustment (not for subjects who discontinue prior to the Week 6 visit)
  - CBC
  - Serum chemistry and eGFR

- Iron indices
- Hepcidin
- C-reactive protein
- VEGF
- Dispense open-label vadadustat (as necessary; only applicable to subjects who are continuing to the open-label extension period)
- Subjects should be questioned regarding dosing compliance
- Review dosing instructions (only applicable to subjects who are continuing to the open-label extension period)

### 9.3.8 Week 14 Visit

At this visit, the following activities/procedures will be performed:

- Vital signs (heart rate and blood pressure should be assessed in a seated position after 5 minutes of rest and prior to blood draws)
- AE review
- Concomitant medication review
- Hb using HemoCue for dose adjustment
- CBC
- Serum chemistry and eGFR
- Dispense vadadustat (as necessary)
- Subjects should be questioned regarding dosing compliance
- Review dosing instructions

### 9.3.9 Week 16 Visit (End-of-treatment visit for the open-label period and early withdrawal visit for withdrawals after Week 10 but before Week 16)

All subjects who received at least 1 dose of open-label vadadustat should complete the Week 16 assessments.

Subjects who withdraw early from the open-label period prior to the Week 16 visit or permanently discontinue study medication prior to the Week 16 visit, should undergo the clinical and laboratory assessments specified below within 1 day of stopping study medication, if possible. Such subjects should also complete the requisite 2-week safety follow-up period (see [Section 9.3.10](#)).

At the Week 16 visit, the following activities/procedures will be performed:

- Vital signs (heart rate and blood pressure should be assessed in a seated position after 5 minutes of rest and prior to blood draws)
- AE review (see [Section 10.3.6](#) for follow-up of unresolved events)
- Concomitant medication review
- Laboratory procedures:
  - Serum pregnancy test for females of childbearing potential (to be analyzed by the central lab)
  - CBC
  - Serum chemistry and eGFR
  - Iron indices
  - Hepcidin

- C-reactive protein
- VEGF
- Subjects should be questioned regarding dosing compliance

#### 9.3.10 Week 18 Safety Follow-Up Visit (Or 2 Weeks after End-of-Treatment Safety Follow-Up Visit)

For subjects randomized to vadadustat who complete the open-label extension period, the safety visit will be conducted 2 weeks after their end-of-treatment visit (Week 16).

For subjects who discontinue the study early during the primary efficacy period or the blinded dose adjustment and data cleaning period, the safety visit will be conducted 2 weeks after their end-of-treatment visit (Week 10).

At the follow-up visit, the following activities/procedures will be performed:

- Vital signs (heart rate and blood pressure should be assessed in a seated position after 5 minutes of rest and prior to blood draws)
- AE review (see [Section 10.3.6](#) for follow-up of unresolved events)
- Concomitant medication review
- Laboratory procedures:
  - CBC
  - Serum chemistry and eGFR

## 10 ADVERSE EVENTS

### 10.1 Definitions

#### 10.1.1 Adverse Events (AEs)

For the purposes of this study, an AE is any untoward medical occurrence (including a clinically significant abnormal laboratory finding) that occurs in the protocol-specified AE reporting period; the event does not necessarily have a causal relationship with that treatment or usage.

An AE includes medical conditions, signs, and symptoms not previously observed in the subject that emerge during the protocol-specified AE reporting period, including signs or symptoms associated with pre-existing underlying conditions that were not present prior to the AE reporting period.

Adverse events therefore include the following:

- All AEs, whether suspected to be causally related to study drug or otherwise.
- All AEs secondary to any medication overdose, medication error, abuse, withdrawal, sensitivity, or toxicity.
- Illnesses apparently unrelated to study drug, including the worsening of a pre-existing illness (see paragraph below on Pre-existing Conditions).
- Injury or accidents. Note that if a medical condition is known to have caused the injury or accident (eg, a fall secondary to dizziness), the medical condition (dizziness) and the accident (fall) should be reported as 2 separate AEs.

- Abnormalities in physiological testing or physical examination findings that require clinical intervention or further investigation (beyond ordering a repeat [confirmatory] test).
- Laboratory abnormalities that require clinical intervention or further investigation (beyond ordering a repeat [confirmatory] test) unless they are associated with an already reported clinical event. Laboratory abnormalities associated with a clinical event reported as an AE (eg, elevated liver enzymes in a subject with jaundice) should be described under ‘Comments’ on the report of the clinical event rather than reported as separate AEs.

The following guidelines are to be used when reporting AEs for this study:

**Medical Diagnoses** – Whenever possible, a medical diagnosis term should be used to report AEs instead of signs and symptoms due to a common etiology, as determined by qualified medical study staff. For example, pneumonia should be the reported AE term, instead of fever, dyspnea, etc., when the diagnosis has been established. Signs and symptoms should be reported as event terms only when the medical diagnosis remains unknown, and revised to a medical diagnosis term once it has been established.

**Procedures** – Diagnostic and therapeutic non-invasive and invasive procedures, such as surgery, should not be reported as AEs. However, the medical condition for which the procedure was performed should be reported if it meets the definition of an AE. For example, an acute appendicitis that begins during the AE reporting period should be reported as the AE and the resulting appendectomy noted under “Comments.”

Pre-planned therapeutic procedures not associated with a new medical condition or worsening pre-existing condition should not be reported as AEs.

**Preexisting Conditions** – In this study, a pre-existing condition (ie, a disorder present before the AE reporting period started and noted on the pre-treatment medical history/physical examination form) should not be reported as an AE unless the condition worsens or episodes increase in frequency during the AE reporting period.

**Abnormal Test Findings** – All laboratory test results will be reviewed by the investigator. The investigator will utilize his/her judgment in determining if out of range laboratory values are clinically significant and should denote this using the abbreviation “CS” on the laboratory report for source documentation. Laboratory tests that are labeled as clinically significant should be reported as AEs, either separately or as part of a description of a symptomatic AE. If there are significant changes in a laboratory report from a previous visit that are determined to be clinically significant, these should also be reported as AEs. Any abnormal laboratory value which requires treatment or further diagnostic testing and/or results in discontinuation from study should be reported as AEs. An expected laboratory abnormality from a condition that is part of the medical history is not considered clinically significant for the purposes of the study unless it represents a worsening of the condition.

**Abnormalities in ALT, AST and Total Bilirubin** – Abnormalities in ALT, AST and total bilirubin should be reported to the sponsor’s medical monitor/medical director or CRO designee within 24 hours of awareness as an SAE with ‘other medically important event’ criterion selected, if the following conditions are met:

- New elevation in ALT or AST > 3 times the upper limit of normal (ULN), with or without an elevation of total serum bilirubin > 2 times ULN, AND
- No other reason was identified that explains the increased ALT/AST with or without an increased bilirubin (eg, viral hepatitis, acute liver disease).

If new elevations in ALT or AST > 3 times ULN, with or without an elevation of total serum bilirubin > 2 times ULN are identified, the following steps are to be taken:

- Temporary discontinuation of study medication.
- Repeat testing of ALT, AST, ALP and total bilirubin, to be completed within 48 to 72 hours to confirm the abnormalities and to determine trend.
- Study medication should not be resumed until monitoring indicates abnormalities have resolved, are stable, or are not rapidly increasing.

**Worsening of Anemia** – In this study, it is possible that some subjects may experience a worsening of anemia. Worsening of anemia should not be considered an AE unless the worsening of anemia is associated with a cause other than the subject's CKD.

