### 7.6.2 Conditions and Documentation of Individual Subject Study Drug Discontinuation

Subjects will discontinue study medication for any of the following conditions:

- Completion of the protocol-defined dosing period (see [Appendix A](#))
- Meets discontinuation criteria related to excess Hb response during the primary efficacy period (defined in [Section 8.2.4](#))
- Major toxicity considered to be related to study medication
- Worsening of anemia requiring ESA rescue or blood transfusion
- Administrative reasons, such as, subject non-compliance or a major protocol violation
- Upon request of the sponsor or regulatory agency
- If, in the opinion of the investigator, it is medically necessary, or if it is the wish of the subject
- Study termination (see [Section 14](#))

Subjects who are taking oral iron supplementation at baseline should continue their oral iron at the same dose throughout their study participation. Changes to oral iron supplementation dose will be considered protocol deviations but will not be considered a reason for subject discontinuation.

The investigator must document the primary reason for discontinuation in the appropriate case report form (CRF).

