### 7.3 Exclusion Criteria

Subjects who meet any of the following exclusion criteria will not qualify for study participation:

1. Anemia due to a cause other than CKD or presence of active bleeding or recent blood loss
2. Sickle cell disease, myelodysplastic syndromes, bone marrow fibrosis, hematologic malignancy, myeloma, hemolytic anemia, thalassemia, or pure red cell aplasia
3. RBC transfusion within 4 weeks prior to or during screening
4. Intravenous iron within 4 weeks prior to or during screening

5. Any ESA use within 6 weeks prior to or during screening (eg, recombinant human erythropoietin, darbepoetin alfa, or methoxy polyethylene glycol-epoetin beta)
6. Aspartate aminotransferase (AST)/serum glutamic oxaloacetic transaminase (SGOT), alanine aminotransferase (ALT)/serum glutamic pyruvic transaminase (SGPT), or total bilirubin  $>2.0 \times$  upper limit of normal during screening. A history of Gilbert's syndrome is not an exclusion criterion.
7. Uncontrolled hypertension (confirmed diastolic blood pressure  $>110$  mm Hg or systolic blood pressure  $>180$  mm Hg) during screening
8. Body mass index (BMI)  $>42.0 \text{ kg/m}^2$
9. Severe heart failure during screening (New York Heart Association Class III or IV)
10. History of untreated proliferative diabetic retinopathy, diabetic macular edema, age-related macular degeneration, central retinal vein occlusion, active retinal hemorrhage, or ongoing ocular treatment with laser photocoagulation or anti-VEGF therapies
11. Acute coronary syndrome (hospitalization for unstable angina or myocardial infarction), surgical or percutaneous intervention for coronary, cerebrovascular, or peripheral artery disease (aortic or lower extremity), surgical or percutaneous valvular replacement or repair, sustained ventricular tachycardia, hospitalization for heart failure, or stroke within 12 weeks prior to or during screening
12. History of active malignancy within 2 years prior to or during screening, except for treated basal cell carcinoma of skin, curatively resected squamous cell carcinoma of skin, cervical carcinoma in situ, or resected benign colonic polyps
13. History of deep vein thrombosis (DVT) or pulmonary embolism (PE) requiring active treatment within 8 weeks prior to or during screening
14. History of hemosiderosis or hemochromatosis

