### 7.6.2 Conditions and Documentation of Individual Subject Study Drug Discontinuation

Subjects will discontinue study medication for any of the following conditions:

- Completion of the protocol-defined dosing period (see [Appendix A](#))
- Meets discontinuation criteria related to excess Hb response during the primary efficacy period (defined in [Section 8.2.4](#))
- Major toxicity considered to be related to study medication
- Worsening of anemia requiring ESA rescue or blood transfusion
- Administrative reasons, such as, subject non-compliance or a major protocol violation
- Upon request of the sponsor or regulatory agency
- If, in the opinion of the investigator, it is medically necessary, or if it is the wish of the subject
- Study termination (see [Section 14](#))

The investigator must document the primary reason for discontinuation in the appropriate case report form (CRF).

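### As worded in the two protocol versions that show Section 10.1.1, the liver restart condition does not bar re-dosing while ALT or AST is above the 3x ULN hold trigger and still rising slowly

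*Protocol*

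**What the plan says.** The protocol file holds three versions. The first two show Section 10.1.1 in full, with the same liver rule in both. The last version breaks off in Section 8.1.4. Its table of contents still lists Section 10.1.1, but the text of that section is not available.

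The rule starts from "If new elevations in ALT or AST > 3 times ULN, with or without an elevation of total serum bilirubin > 2 times ULN". Study drug is then stopped temporarily, and ALT, AST, ALP and total bilirubin are repeated, "to be completed within 48 to 72 hours to confirm the abnormalities and to determine trend". The restart condition follows: "Study medication should not be resumed until monitoring indicates abnormalities have resolved, are stable, or are not rapidly increasing". No enzyme or bilirubin level is attached to the restart, no rate is attached to the word for fast, and the same condition applies whether or not bilirubin is also raised.

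Elevations with no other identified cause must be reported within "24 hours of awareness as an SAE with" the criterion for other medically important events. Section 7.6.2 lists general reasons to stop study drug, among them "Major toxicity considered to be related to study medication", a request from the sponsor, and "If, in the opinion of the investigator, it is medically necessary, or if it is the wish of the subject".

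**The concern.** The hold shows that the sponsor regards ALT or AST above 3x ULN as a reason not to continue dosing for the time being. One would expect the restart condition to ask for some evidence that the problem has passed or at least settled. Because the three alternatives are joined by 'or', the weakest one decides. A site that judges the Section 7.6.2 stops not to be met could follow the sentence exactly and re-expose a subject whose values are still above the trigger and getting worse, including one whose bilirubin is also above 2x ULN.

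The protocol is more definite for hemoglobin. Section 8.2.7 gives a level at which to interrupt (above 13.0 g/dL), a level at which to resume (12.5 g/dL or below) and an example of a rapid rise (more than 1 g/dL in 2 weeks). For the liver it gives an interruption level only, and about 25 sites would each decide what counts as rapid.

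**Working it through.** The protocol states no figure to reproduce here, and nothing depends on sample size or alpha. The check is one of logic, with simple arithmetic for scale.

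**Step 1. Inputs.** From Section 10.1.1: the hold trigger (ALT or AST above 3x ULN, bilirubin above 2x ULN or not) and the three restart alternatives. From Section 7.3, criterion 6: the entry limit of 2.0x ULN for AST, ALT or total bilirubin. From Section 6.1: about 25 sites.

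**Step 2. Reduce the condition.** Call the alternatives R (resolved), S (stable) and N (not rapidly increasing). A resolved value and a stable value are both not rapidly increasing, so R and S lie inside N, and R or S or N = N.

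**Step 3. Count states.** Cross four trends with three levels, 4 x 3 = 12 states, taking 'resolved' to mean back to normal without a rapid rise. 'Open' means that the sentence does not bar restart.

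| Trend after the hold | Normal | 1 to 3x ULN | Above 3x ULN |
|---|---|---|---|
| Falling | open | open | open |
| Stable | open | open | open |
| Slow rise | open | open | open |
| Rapid rise | barred | barred | barred |

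Nine states are open and three barred. Applying N alone gives the same answer in all 12. A slow rise above 3x ULN is among the open states.

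**Step 4. The same count without the third alternative.** With R or S only, the three non-rapid states at normal level stay open, as do stable at 1 to 3x and stable above 3x: 3 + 2 = 5. The four that close are falling and slowly rising at 1 to 3x, and falling and slowly rising above 3x: 9 - 4 = 5. Every rising state above normal is now barred. A stable value above 3x ULN is still open. On a strict reading, a falling value has to wait until it settles or resolves.

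**Step 5. Scale.** Trigger against entry limit: 3.0 / 2.0 = 1.5. As an illustration with assumed values, take a subject held at 3.5x ULN whose retest is 5%, 10% or 20% higher:

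- 3.5 x 1.05 = 3.68x ULN
- 3.5 x 1.10 = 3.85x ULN
- 3.5 x 1.20 = 4.20x ULN

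All three exceed 3.0 and, with no rate given, none is clearly barred. A 5% change could fairly be called stable, so the last two carry the example.

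**Step 6. Look for another barrier.** No other text shown sets a liver restart level or requires the sponsor's agreement to restart. Section 10.1.1 gives no retest interval after restart, and in Appendix A scheduled chemistry is 4 weeks apart from Week 6 to Week 10 and again from Week 10 to Week 14.

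**The case against.** The strongest reply is that the sentence sets a minimum and permits nothing by itself. The retest is ordered to establish the trend, so clinical judgement is evidently the design, and other sections surround it. For an unexplained elevation, Section 10.3.3 requires both the SAE and its follow-up information to reach the medical monitor or CRO designee within 24 hours, with close observation until the condition resolves or settles. Section 10.3.6 continues SAE follow-up after participation ends. Section 10.3.4 names hepatic injury as an example of an event pointing to drug causality, which makes the mandatory Section 7.6.2 stop for related major toxicity more likely to apply to the worst case. The sponsor would see the trend and could require a stop.

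Most of that stands, and it limits the point. A reader might infer that sites are told to restart, or that a site decides alone. The documents do not support either reading for unexplained elevations. What remains is that these provisions concern reporting, observation and judgement, and none bars a restart. An elevation put down to another cause, such as viral hepatitis, falls outside the special 24-hour rule yet meets the same restart condition.

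A reader might also see a contradiction with the entry limit of 2.0x ULN. There is none: that limit applies at screening, and the ratio of 1.5 only gives scale.

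The second reply is that the wording is shown only in versions that a later one has replaced. That is correct. The last version was edited elsewhere (Section 7.6.2, for instance, lost a paragraph on oral iron), so the wording cannot be presumed unchanged.

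**Conclusion.** The point holds in a limited form. In the two versions that show it, the restart condition amounts to not rising rapidly, with no rate. It does not bar re-dosing above 3x ULN during a slow rise, with or without bilirubin above 2x ULN. It stops 3 of 12 states where a condition of resolved or stable would stop 7.

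This rests on the ordinary meaning of the three alternatives and on the absence of a liver restart level in the text shown. It remains to be confirmed that the sentence is still in Section 10 of the last version. How often it would matter is unknown, because the documents give no frequency of such elevations.

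A reader might conclude that the protocol must adopt 3x and 2x ULN as restart ceilings. The documents give those values as hold and reporting thresholds, never as restart levels. A ceiling would also keep off drug a subject with a stable, explained elevation. That is a trade-off for the sponsor to weigh. This is a safety wording correction worth making, with no effect on power or type I error.

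**What to change.** First confirm that the sentence is still in Section 10.1.1 of the last version. If it is, delete the third alternative, so that restart requires abnormalities that have resolved or are stable on repeat testing.

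The cost is one sentence, with no added scheduled visits, staff or subjects. A few subjects would stay off drug longer and need some unscheduled liver tests, including those whose values are falling but have not yet settled. Each such subject is 1 of 12 in an arm (1 / 12 = 8.3%) and would have less exposure if the hold falls in the 6-week primary efficacy period.

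As an option outside the required change, the sponsor may add ceilings for restart: ALT and AST at or below 3x ULN and total bilirubin at or below 2x ULN. Criterion 6 in Section 7.3 ends with "upper limit of normal during screening. A history of Gilbert's syndrome is not an exclusion criterion", so a subject with that condition could wait longer under a bilirubin ceiling.
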